## 1. AMENDMENTS FROM PREVIOUS VERSION(S)

Not applicable.

## 2. INTRODUCTION

This document describes the planned statistical analyses for Protocol B7501001. This analysis plan is meant to supplement the study protocol. In this document, any text taken directly from the protocol is italicized. Any deviations from this analysis plan will be described in the Clinical Study Report (CSR).

### 2.1. Study Design

*This is a Phase 1, open label, multi-center, single arm, non randomized, multiple dose, safety, pharmacokinetic (PK) and pharmacodynamic (PD) study of single agent PF-06650808 in sequential cohorts of adult patients with advanced solid tumors for whom no standard therapy is available. Successive cohorts of patients will receive escalating doses of PF-06650808 intravenously every 21 days starting at a dose of 0.2 mg/kg.*

*Approximately 55 patients are expected to be enrolled in the study at approximately 3-4 sites. The actual number of patients enrolled will depend upon tolerability of PF-06650808 and the number of dose levels required to identify the MTD.*

*The study will include two parts, a dose escalation phase (Part 1) followed by a dose expansion phase (Part 2). Part 1 will estimate the MTD in dose escalation cohorts in patients with advanced solid tumors for whom no standard therapy is available in order to establish the RP2D. Part 2 will include approximately 20 patients with TNBC enrolled at the MTD in order to explore benefit from treatment as suggested by preclinical findings, and will better define the safety profile at the RP2D. Additional safety information gathered in Part 2 may be used to modify the dose recommended for future Phase 2 studies.*

*The study is expected to be completed in approximately 24 months. The end of the study is the last visit of the last patient.*

### 2.2. Study Treatment

*A modified continual reassessment method (mCRM) targeting a DLT rate of 25% will be utilized for Part 1 (dose escalation phase). Patients will be enrolled in cohorts of 2 to 4, starting with 0.2 mg/kg for the first cohort. The possible doses explored will be from a fine grid of doses ranging from 0.2 mg/kg to 6.4 mg/kg. If a high DLT rate is observed at the starting dose of 0.2 mg/kg, a lower dose such as 0.14 mg/kg or lower will be considered. The study may be stopped if the drug is deemed not tolerable at the lowest reduced dose.*

*Patients will continue with study treatment every 21 days until disease progression, withdrawal of consent, unacceptable toxicity occurs, or the study is terminated. Patients experiencing a DLT may be managed with dose modification or discontinuation.*

*Part 2 will include patients enrolled at the MTD in order to explore benefit from treatment and will better define the safety profile at the RP2D.*

## 2.3. Study Objectives

### ***Dose Escalation (Part 1) Objectives***

*Primary Objective:*

- *To assess safety and tolerability at increasing dose levels of PF-06650808 in patients with advanced solid tumors unresponsive to currently available therapies, or for whom no standard therapy is available in order to determine the Maximum Tolerated Dose (MTD) and select the Recommended Phase 2 Dose (RP2D).*

*Secondary Objectives:*

- *To evaluate the overall safety profile.*
- *To characterize the single and multiple dose pharmacokinetics of ADC (PF-06650808), total antibody (PF-06460005) and unconjugated payload (PF-06380101).*
- *To evaluate the immunogenicity of PF-06650808.*
- *To document any preliminary evidence of anti-tumor activity.*

CC1 [REDACTED] :

- CC1 [REDACTED]

### ***Dose Expansion (Part 2) Objectives***

*Primary Objective:*

- *To confirm safety and tolerability and explore preliminary evidence of anti-tumoractivity of PF-06650808 at the RP2D in patients with TNBC.*

*Secondary Objectives:*

- *To evaluate the overall safety profile at the R2PD.*
- *To characterize the single and multiple dose pharmacokinetics of ADC (PF-06650808), total antibody (PF-06460005) and unconjugated payload (PF-06380101).*
- *To evaluate the immunogenicity of PF-06650808.*

CC1 [REDACTED] :

- CC1 [REDACTED]

### 3. INTERIM ANALYSES, FINAL ANALYSES AND UNBLINDING

No interim analysis or blinding is planned for this study. The final analysis will be conducted after the last subject last visit (LSLV).

### 4. HYPOTHESES AND DECISION RULES

#### 4.1. Statistical Hypotheses

There are no statistical hypotheses. The emphasis of the final analyses will be on estimation of key summary statistics.

#### 4.2. Statistical Decision Rules

##### 4.2.1. Part 1

*A modified continual reassessment method (mCRM) targeting a DLT rate of 25% will be utilized for Part 1 (dose escalation phase) (Goodman et al, 1995; O'Quigley et al, 1990). Patients will be enrolled in cohorts of 2 to 4, starting with 0.2 mg/kg for the first cohort. The possible doses explored will be from a fine grid of doses ranging from 0.2 mg/kg to 6.4 mg/kg. If a high DLT rate is observed at the starting dose of 0.2 mg/kg, a lower dose such as 0.14 mg/kg (a 30% reduction from starting dose) or lower will be considered. The study may be stopped if the drug is deemed not tolerable at the lowest reduced dose. The mCRM model will determine the next dose level based on the DLT rate using a 30%, 69% and 100% dose increment for 0, 1 or 2 dose skips respectively.*

*Starting with the second cohort, patients will be assigned to a dose that is closest to the current MTD prediction based on a model that mCRM utilized to learn about overall dose-toxicity relationship. This model is updated after DLT assessment of each cohort. At any given point in this phase, doses can be escalated, deescalated, unchanged or revisited, but always aiming towards the target MTD. To prevent overly aggressive dose-escalation, the maximum allowed dose increase will be limited to 2 increments at a time (ie, no more than 100% dose increase at a time). In addition, if two clinically significant Grade 2 toxicities of the same type are seen in a cohort, dose escalation will be limited to no greater than 69% for the next cohort. If there is one additional case of the same Grade 2 toxicity or two other cases of clinically significant Grade 2 toxicities of the same type, dose escalation will again be limited to no greater than 69% for the next cohort; otherwise dose escalation following the mCRM algorithm will resume. Grade 2 toxicities will not be considered clinically significant if a corresponding Grade 3 toxicity exists (by NCI CTCAE v 4.03); Grade 2 toxicities without a corresponding Grade 3 toxicity will be considered clinically significant (eg, Grade 2 alopecia, dry skin, libido decrease). In addition, Grade 2 nausea, vomiting, and diarrhea will not be considered clinically significant unless it has been optimally medically managed.*

*The combination of a fine dose grid and the ability to skip doses allows rapid dose escalation if no DLTs are observed and small dose changes with exploration of adjacent doses once the observed DLT rate becomes noticeable. The algorithm will stop if any of the following criteria is met:*

1. *The maximum sample size has been achieved (approximately 35 patients total).*

2. *At least 6 patients have been accumulated on a dose that is predicted to be the MTD and there are at least 12 patients overall enrolled in the trial, or*
3. *All doses explored appear to be overly toxic and the MTD cannot be determined in the current trial setting.*

*Although dose levels are capped at 6.4 mg/kg, this mCRM will continue to operate subject to the constraints detailed above while allowing for doses higher than specified. Doses may continue to be skipped, visited more than once, or not visited at all. In addition, if necessary, doses beyond 6.4 mg/kg may be allowed in 30% increments.*

*All significant AEs and serious adverse events (SAEs) will be reviewed by the sponsor and investigators to determine if the dose allocation schedule requires modification. The cohort steering committee, comprised of the sponsor clinical team and the investigators, can override the dose escalation increment determined by the algorithm if a more conservative approach is mandated.*

*Patients will continue with study treatment every 21 days until disease progression, patient refusal or unacceptable toxicity occurs. Patients experiencing a DLT may be managed with dose modification or discontinuation.*

*Subsequent dose levels may not be opened until all patients entered at the current dose level have been treated and observed for at least one complete cycle (through Day 21) and the number of DLTs among those patients in their first cycle has been determined.*

#### **4.2.2. Part 2**

*Part 2 of this study is intended to confirm the safety and tolerability of the dose selected in Part 1 while assessing the antitumor activity of ADC (PF-06650808) in TNBC patients. Patients in the expansion cohort will be pre-selected according to their target tumor expression using archival tumor tissues. Only patients with relatively high target expression will be selected. The DLT rate and its 95% confidence interval at the selected dose may be estimated.*

*Analyses may be performed on data from both Part 1 and Part 2 to explore the relationships between PK parameters, safety endpoints, and efficacy endpoints.*

### **5. SAMPLE SIZE DETERMINATION**

*Approximately 55 patients are expected to be enrolled in this study.*

*Similar to the conventional 3+3 design, the exact sample size of the CRM design in Part 1 cannot be pre-specified in advance due to the dynamic feature of the design. The minimum and maximum sample sizes after which the Part 1 can be stopped and MTD declared are approximately 12 and approximately 35 patients, respectively. Also, a minimum of 6 patients treated at the MTD dose in Part 1 is required to establish such dose as the RP2D. The actual sample size of Part 1 will depend on the underlying dose toxicity profile and variability in actual data realization.*

*As for the number of patients treated at each dose, it is expected that the typical number will be 2 to 4 patients for the doses actually studied. For the dose declared as MTD at the end of Part 1, this number will be 6 or more patients. However, since not every dose listed will be studied and variable cohort size is allowed, the actual number of patients treated at each dose will vary.*

*The sample size in Part 2 is based on clinical consideration, rather than statistical justification. Upon identification of the MTD by the mCRM method, approximately 20 patients with triple negative breast cancer will be enrolled in Part 2 to further evaluate safety and preliminary efficacy parameters.*

CC1

## **6. ANALYSIS SETS**

Several analysis sets are defined and will be considered for this study.

### **6.1. Full Analysis Set**

*The full analysis set includes all enrolled patients. This is equivalent to the ITT (intent-to-treat) population.*

### **6.2. ‘PER PROTOCOL’ Analysis Set**

*The per protocol analysis set includes all enrolled patients who receive at least one dose of study medication at the dose level of RP2D and who do not have major treatment deviations during first cycle. Patients with major treatment deviations in Cycle 1 are not evaluable for the RP2D assessment. Major deviations include failure to satisfy major entry criteria (eg, confirmation of the target disease; signed informed consent) or use of other anticancer treatments during the active treatment and disease follow-up phases other than as defined/allowed in this protocol. A baseline disease assessment and at least one post-baseline disease assessment are appropriate to allow efficacy analysis.*

### **6.3. Safety Analysis Set**

*The safety analysis set includes all enrolled patients who receive at least one dose of study medication.*

### **6.4. PK Analysis Set**

[figure not shown]
#### **6.4.1. PK Concentration Set**

The PK concentration population is defined as all treated patients who have at least 1 concentration measured.

## 6.4.2. PK Parameter Set

The PK parameter analysis population is defined as all enrolled patients treated who have sufficient information to estimate at least 1 of the PK parameters of interest.

CCI

## 6.6. Other Analysis Sets

### 6.6.1. Modified Intent-to-Treat Set

*The modified intent-to-treat (mITT) is the analysis population that will follow the ITT principle and include subjects receiving at least 1 dose of study medication with baseline assessment and at least 1 post baseline assessment or disease progression or death before the first tumor assessment. The mITT population may be used for occasions such as conference presentation when the study is still ongoing.*

## 6.7. Treatment Misallocations

Subjects who receive the wrong initial dose for whatever reason will be analyzed according to the initial dose actually received. Subjects who receive the wrong dose after the initial dose will be analyzed according to the initial dose received.

## 6.8. Protocol Deviations

All deviations will be listed in the CSR. Major treatment deviations include, but are not limited to, less than 80% of the planned Cycle 1 PF-06650808 dose provided the reduction/omission is not due to treatment-related toxicity. Subjects with major Cycle 1 treatment deviations are not evaluable for MTD.

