9.2. Statistical Methods and Properties

9.2.1. Part 1

Part 1 of this study employs a modified continual reassessment method (mCRM) targeting a DLT rate of 25% to estimate the MTD. The mCRM algorithm utilizes Bayesian

methodology to consistently learn about dose-toxicity relationship after each cohort's DLT response becomes available. The underlying model assumption is that DLT rate at each dose can be expressed as $\text{Pr}(\text{DLT} | x) = f(x, \beta)$, where x is a quantity associated with a dose, f is a monotonically increasing function, and β is an unknown parameter with prior distribution placed on it at the beginning of the trial. The first cohort of (2-4) patients will be assigned to 0.2 mg/kg. After the first cohort's response becomes available (all patients through Day 21), the prior distribution of β is updated based on their DLT responses and becomes a posterior distribution. The current estimate of MTD is as the dose corresponding to $x = f^{-1}(0.25, \beta)$, given posterior information about β (ie, DLT data + modeling), and the next cohort's dose assignment is chosen as the dose closest to this estimated MTD but not exceeding it. This process is continued until 1 of the stopping rules below is triggered.

1. Maximum sample size of 35 patients has been reached.
2. MTD has been identified with sufficient accuracy: at least 6 patients have been accumulated on a dose that is currently estimated to be the MTD and there are at least 12 patients overall enrolled in the trial.
3. All doses appear to be overly toxic and the MTD cannot be determined in the current trial setting.

Starting from the second cohort and until the end of trial, the above described mCRM algorithm constantly incorporates additional information about dose-DLT relationship learned from the data via modeling and that is reflected on the projected MTD. By design, such dose allocation procedure will eventually cluster dose assignments around the dose yielding an approximately 25% DLT rate. Because CRM derives MTD estimate from all the data accumulated at a given time and not just the last cohort's response, the procedure is capable of incorporating DLT information occurring late in the trial, ie, after the minimum required DLT follow-up of 21 days.

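### SAP 6.8 makes patients with a major Cycle 1 treatment deviation non-evaluable for the MTD with no exception for one who had a DLT, other sections point the other way, and no section names the data set that feeds the mCRM

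*SAP*

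**What the plan says.** **Sections that exclude.** SAP 6.8 states "Subjects with major Cycle 1 treatment deviations are not evaluable for MTD". Its list of major deviations is open-ended, and the one example is "less than 80% of the planned Cycle 1 PF-06650808 dose provided the reduction/omission is not due to treatment-related toxicity". SAP 6.2 says "Patients with major treatment deviations in Cycle 1 are not evaluable for the RP2D assessment" and gives further grounds: "Major deviations include failure to satisfy major entry criteria", or use of anticancer treatment that the protocol does not allow. Protocol 9.1 (item 4) has the same text and labels the set as the one evaluable for MTD. None of the three mentions a patient who had a DLT.

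**Sections that include.**
- SAP 9.2.1 summarises Part 1 DLTs on the Safety Analysis Set, which is every patient who received at least one dose.
- Protocol 9.2.1 says the CRM estimates the MTD from all data accumulated so far.
- SAP 4.2.1 and Protocol 3.2 open a new level only when the patients entered at the current one have been observed and "the number of DLTs among those patients in their first cycle has been determined".
- SAP 6.7 says "Subjects who receive the wrong initial dose for whatever reason will be analyzed according to the initial dose actually received".

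**The model.** Protocol 9.2.1: "Part 1 of this study employs a modified continual reassessment method (mCRM) targeting a DLT rate of 25% to estimate the MTD". It assumes that "f is a monotonically increasing function".

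**The concern.** A deviation can make a DLT-free patient uninformative: someone given 70% of the dose who has no DLT says little about the full dose. It does not in the same way cancel a DLT that was observed. Under the plan's own monotone model, a DLT on less than the planned dose is at least as strong evidence against the planned dose as a DLT on all of it. SAP 6.8 treats the two patients alike.

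The toxicity carve-out does not close the gap. It concerns why the dose was short, not what happened afterwards. It protects neither a DLT that follows an error-related short dose nor a DLT in a patient who failed a major entry criterion.

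The MTD is the main output of Part 1, and about 20 Part 2 patients are to be treated at it. The trial is open label and the deviation list is open-ended, so without a fixed rule evaluability could be decided after the DLT outcome is known.

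**Working it through.** **1. The plan's own figure.** Part 1 maximum 35 + Part 2 about 20 = about 55, as Protocol 9.3 and SAP 5 state. It does not depend on the evaluability rule, and no figure in the plan does.

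**2. Which set feeds the mCRM?** The Safety Analysis Set is named for the DLT summary table (SAP 9.2.1), not for the model. The per-protocol set cannot be the model input as written: it holds only patients dosed at the RP2D level, which is unknown during escalation. SAP 6.8 states who is not evaluable for MTD but defines no set. The input is therefore undefined.

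**3. When the rule would apply.** Protocol 5.2.3 gives one infusion per cycle, on Day 1. A Cycle 1 dose below 80% must come from that infusion, for example through a preparation or pump error. The documents give no frequency for this.

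**4. Effect of one patient on the crude rate.**

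| DLTs/patients | Drop one deviator with a DLT | Drop one DLT-free deviator |
|---|---|---|
| 2/6 = 33% | 1/5 = 20% | 2/5 = 40% |
| 1/3 = 33% | 0/2 = 0% | 1/2 = 50% |
| 3/12 = 25% | 2/11 = 18% | 3/11 = 27% |

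Six patients at the MTD are enough to declare it (Protocol 9.3), so the first row is realistic in size.

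**5. Effect of one patient through a CRM.** The plan's text gives no model form or prior curve, so these are assumed: power model; grid 0.2 × 1.3^k mg/kg; prior MTD 1.6 or 3.2 mg/kg; normal prior SD 1.16 or 2.0; tested dose 1.63 or 2.12 mg/kg. Data: 10 DLT-free patients at lower doses, 1 DLT in 5 at the tested dose, and one further DLT patient given 70% of it. Keeping that patient at the dose received puts the estimated DLT rate at the tested dose at 18–25%; dropping the patient gives 10–15%. The model MTD rises by one or two grid steps (30% or 69%). Every case presupposes that the dropped patient had a DLT, so this shows the effect of such a loss, not how often it happens.

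**6. Expected effect of the rule.** Let p be the true DLT rate, and q0 and q1 the chance of a major deviation without and with a DLT (both assumed).
- Literal SAP 6.8: p(1−q1) / [p(1−q1) + (1−p)(1−q0)]
- Exclude only DLT-free deviators: p / [p + (1−p)(1−q0)]

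With p = 25%:

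| q0 / q1 | Literal 6.8 | Exclude only DLT-free deviators |
|---|---|---|
| 5% / 5% | 25.0% | 26.0% |
| 10% / 10% | 25.0% | 27.0% |
| 5% / 20% | 0.2000/0.9125 = 21.9% | 26.0% |
| 10% / 30% | 0.1750/0.8500 = 20.6% | 27.0% |
| 20% / 10% | 0.2250/0.8250 = 27.3% | 29.4% |

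**7. Simulated true DLT rate at the selected MTD.** 3,000 runs per scenario; power model, prior variance 1.34; cohorts of 3; steps of at most 100%; stop at 6 on the MTD with at least 12 overall, or at 33 patients (whole cohorts under the cap of 35). Each range covers two assumed true curves, with MTD 1.2 or 2.4 mg/kg. Patients enter at the assigned dose.

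| q0 / q1 | Keep everyone | Literal 6.8 | Exclude only DLT-free deviators |
|---|---|---|---|
| 10% / 10% | 25.4–26.7% | 25.1–25.6% | 23.2–24.3% |
| 5% / 20% | 25.2–26.4% | 27.7–29.0% | 24.3–25.2% |
| 10% / 30% | 25.2–26.2% | 29.1–30.6% | 23.2–24.0% |

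When deviations are commoner with a DLT, the literal rule adds 2.5 (27.7 − 25.2) to 4.4 (30.6 − 26.2) percentage points against keeping everyone. When they are unrelated, it adds nothing.

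**The case against.** A reader might infer that the plan discards DLTs and so biases the MTD upward. The documents support neither half of that.

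- **Discarding is not settled.** SAP 9.2.1, Protocol 9.2.1 and SAP 4.2.1 all fit a count of every treated patient. SAP 6.7 and 6.8 can also be read together, one assigning the dose group and the other deciding evaluability. This stands: the defect is an unreconciled rule. But the only sentences that address MTD evaluability directly are the excluding ones, and a statistician who followed them would drop the patient.
- **Upward bias does not follow in general.** The rule also removes DLT-free deviators. It is neutral when deviations are unrelated to DLTs, and pushes the MTD down when they are commoner without a DLT (27.3% above). The most obvious link between toxicity and deviation, under-dosing for toxicity, is already carved out. This stands.
- **Not every DLT in a deviator is informative.** The monotonicity argument covers under-dosing only. The DLT criteria exclude events related to progression but do not require attribution to study drug, so keeping every DLT whatever the deviation would count a toxicity that arose after prohibited chemotherapy. This stands and limits the fix. Likewise, starting new therapy after a DLT and discontinuation is not clearly a deviation, because Protocol 5.4.1 bars it only while study therapy is being given.
- **The events stay visible.** DLTs and deviations are listed, and the steering committee can override the algorithm in the conservative direction. That lowers the risk but leaves the model input undefined.

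**Conclusion.** The concern holds in limited form. SAP 6.8, SAP 6.2 and Protocol 9.1 (item 4) contain an exclusion with no DLT exception. It is not reconciled with SAP 9.2.1, 4.2.1 and 6.7 or with Protocol 3.2 and 9.2.1, and the set feeding the mCRM is unnamed. Applied literally, the rule can remove an informative DLT, and at these sample sizes one removal is enough to take the observed rate from above the 25% target to below it.

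The MTD is biased upward only if major deviations are commoner in patients with a DLT. At assumed rates of 5%/20% and 10%/30%, the true DLT rate at the selected dose rises by about 2.5 to 4.4 points. Those deviation rates, the model, the prior and the true curves are assumptions, so the simulation shows direction and rough size only. The gap in the text does not depend on them.

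**What to change.** In SAP 6.8 and 6.2 and Protocol 9.1 (item 4), define the DLT-evaluable set that feeds the mCRM, and refer to it in SAP 9.2.1 and Protocol 9.2.1:

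- A treated patient with a Cycle 1 DLT that arose before any prohibited anticancer treatment is evaluable and enters the mCRM at the dose actually received (SAP 6.7).
- A DLT-free patient with a major Cycle 1 treatment deviation is not evaluable.
- A DLT that arose after prohibited anticancer treatment is reviewed case by case, and the MTD estimate with and without it is shown in a sensitivity run.

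The Part 1 DLT summary can stay on the Safety Analysis Set if the SAP says that it is a reporting table and not the model input.

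**Cost.** A few sentences in each document, and a model that can accept a dose off the grid. The rule leans slightly conservative: keeping every DLT while dropping DLT-free deviators gives an expected evaluable rate of about 26–27% at a true 25% with assumed deviation rates of 5–10%. In the simulation with 10% deviations unrelated to DLTs, it selects doses with a true rate of 23.2–24.3%, a little further below target than the literal rule (25.1–25.6%) is above it. The SAP should state this trade-off.
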